The potential direct benefits include improved health as a result of exercise training and potential educational benefits associated with current health status, healthy eating, and exercise/physical activity. Each participant may gain knowledge of current health status as determined by medical history and physical examination as well as health benefits related to monitoring of their diabetes. The benefit to society will include an improved understanding of the mechanisms of type 2 diabetes (T2DM) development and the treatment of diabetes and reduction of cardiovascular disease risk. Data from this study may also help determine an effective approach to prevent the progression of obesity and obesity-related diseases and inflammatory conditions. The minimal potential risks are outweighed by the benefit of the information that will be acquired from this study.

Study Objectives

1) Test the effects of chronic aerobic exercise versus standard care alone on sRAGE in the circulation of adults with T2DM.

2) Test the effects of chronic aerobic exercise versus standard care alone on RAGE in skeletal muscle of adults with T2DM.

Study Outcomes

The global construct of this study is to provide insight into the role of aerobic exercise on muscle health in the context of RAGE biology. Due to the implication of RAGE signaling, findings of this study may guide the development of therapeutic modalities for T2DM.

Study Hypotheses

[figure not shown]
Our central hypothesis is that skeletal muscle contributes to sRAGE appearance in the circulation and maintenance of healthy levels of total sRAGE promotes cardiometabolic health. Therefore, two specific working hypotheses have been proposed.

- 1) Circulating sRAGE levels will increase following 12-weeks of aerobic exercise training and this change will be related to reduced muscle RAGE expression and increases in insulin sensitivity and cardiorespiratory fitness.
- Skeletal muscle expression of RAGE will decrease following 12-weeks of aerobic exercise training and this change will be related to increases in circulating sRAGE, insulin sensitivity, and cardiorespiratory fitness.

STUDY DESIGN

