A total of 60 adults, (approximately 30 males and 30 females) will complete this study. Subjects must be weight stable (± 2 kg for ≥ 6 months), sedentary (<30 min of exercise, 3 times per week), and free of any additional contraindications to participation in exercise testing or the training. Selection criteria will limit confounding influence on the study objectives and exclude subjects with conditions that may have unknown effects on metabolic function and the outcomes proposed or the ability to participate in the aerobic exercise intervention or testing procedures. Criteria will be reviewed by the research team and/or study physician and eligibility to participate will be determined on a case by case basis.

Subject Inclusion Criteria

- Age 40-75 y
- Type 2 diabetes
- Overweight or obese (BMI 26-44 kg/m²)
- Fluency in English (written and verbal)

Subject Exclusion Criteria

- Age <40 or >75 y
- BMI <26 or >44 kg/m²
- Existing cardiovascular, cerebrovascular, renal, or hematological disease, cancer, or other metabolic diseases that is suspected to impact study outcomes
- Current use of tobacco
- Pregnant or lactating

Strategies for Recruitment and Retention

Subjects will be recruited from the greater Ann Arbor area through multiple mechanisms. Primarily, study advertisements will be posted and distributed throughout the communities surrounding the University of Michigan. In addition, we will utilize our clinical collaborations within the Division of Endocrinology and Metabolism to strengthen our ability to identify and recruit potential volunteers. We plan to advertise and seek potential volunteers through word of mouth, the Data Office for Clinical and Translational Research, MDRC Diabetes Research Registry, the website of the School of Kinesiology, newspaper, postal mail, and social media outlets. In our previous studies, we have not experienced difficulty recruiting individuals for muscle biopsy or metabolic procedures.

Screening Procedures

Initial screening of participants will occur via a website screening tool or telephone interview. During this time, the study will be described in detail and we will obtain information about age, body mass index (BMI), smoking and physical activity status, current medical conditions, health status and medications, along with other eligibility

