Group Assignment Procedure

Following enrollment into the study, participants will be randomized into either the Aerobic Exercise group (n=30) or Control group (n=30. Females and males will be equally distributed between the groups. Regardless of group assignment, each participant will receive standard care for diabetes management.

Aerobic Exercise Training

Every AE training session will be supervised by the research team using established protocols [22-28]. Training sessions will take place at the Central Campus Recreation Building (CCRB), Domino Farms, or other University of Michigan recreation facility (e.g., North Campus Recreation Building) approximately 5 days per week and include treadmill walking, cycling, elliptical, or other related modes of exercise. Briefly, AE training will begin with a 2-week ramp-up, familiarization period of progressing exercise intensity and duration. Training intensity will progress from 55% VO₂max for week 1 (40 min session), to 60-65% VO₂max for week 2 (50 min session), to ~70% VO₂max for all other weeks (50 min session). Subjects will perform a brief warm-up and cool-down (~5 min each) that may include stretching or other light exercises for a total exercise time of 60 min. Subjects will wear heart rate monitors during each training session to provide real-time feedback of target heart rate. Intensity, duration, resting and exercise heart rates, and blood pressures will be recorded for each session. Exercise duration and intensity may be adjusted at the discretion of the PI, Co-I, or study team member. Followup VO₂max tests will be performed at approximately weeks 4 and 8 to monitor progress. AE intensity will be adjusted to match the prescribed training intensity [23, 24, 29-32]. Subjects in the AE training group will also conduct foot safety checks with the research team to monitor foot ulcers/blisters. Relevant findings during foot inspections will be addressed with the participant and study physician. Non-weight bearing exercise may be implemented if the subject is limited.

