Concomitant Medications

[figure not shown]
Subjects participating in this study will be diagnosed with T2DM and therefore have unique medical needs. In addition to the screening provided in this study, each participant will be encouraged follow their personal physician's guidance. Prior to and during the intervention period, all medication use, dose and frequency will be documented

Assessment of Subject Compliance with Study Intervention

Subject compliance will be regularly assessed and documented by the research team. Participants enrolled in the AE group will have contact with the research team approximately 5 days per week and the Control group will have contact with the research team approximately twice per month. Compliance will be determined through routine personal communication and primarily evaluated based on exercise training attendance (Aerobic Exercise group only), physical activity tracking, and dietary monitoring. Subjects in the Aerobic Exercise group are expected to complete \geq 80% of the training sessions over the course of the 12 weeks.

STUDY SCHEDULE AND PROCEDURES

Figure 3 provides a brief study summary of the study schedule. This study is composed of initial subject screening and enrollment based on established inclusion and exclusion criteria and randomization to 12 weeks of Aerobic Exercise training or Control Period (both including established Standard Care practices). Participants will all complete the same baseline testing and final study visit testing. Subjects randomized to the AE group will also undergo follow-up testing at weeks 4 and 8 (\pm 1 week) to adjust exercise training parameters. All testing will occur at the Michigan Clinical Research Unit (MCRU), Michigan Nutrition Obesity Research Center (NORC), Domino Farms, Frankel Cardiovascular Center (CVC), and/or Central Campus Recreation Building (or other University recreation building) and based on subject schedules, will include a total of approximately 7 visits.

Scheduling Flexibility

Due to limitations of the subject's schedule, study team, experimental approach, and/or clinic availability, some procedures may be excluded or adjusted from any given visit. Excluded or adjusted procedures will be at the discretion of the PI or Co-I and will not be considered a protocol deviation.

Subject Screening

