The primary outcomes of this study involve collecting data at pre-aerobic exercise training and 12 weeks of training. Comparisons of trajectories across groups (training vs. Control) over time are made with appropriate adjustments for fixed (age, sex, medications, diabetes duration and severity) and time-varying covariates (i.e., weight, BMI, etc). Because of the anticipated nonlinear response curves of outcome variables we will use nonlinear mixed effects models to analyze our data. Using PROC NLMIXED in SAS 9.2 (SAS Inc.) we will fit the nonlinear models using two likelihood-based methods: adaptive Gaussian guadrature and a first-order Taylor series approximation [54-56]. The nonlinear mixed model is: $y = f(x_{ij}, \beta, u_i) + e_{ij}$, where f is some nonlinear function of known vector covariates (xij) for the jth observation on the jth subject, unknown fixed effect parameters (β), an unknown vector of random effect parameters (u_i), and unknown random errors (eii). For this study, we will treat training group as main fixed effect, intercept as random effects, and all outcomes will be used as responsive variables. Using nonlinear mixed effects models described above, we will reject null hypothesis if significant (p<.05) interaction effect between group and time is observed. Post-hoc analysis will examine differences between groups at different time points to assess the effect of exercise training on the outcome variables across time during the intervention. Our human sample size was determined using data from preliminary studies to provide adequate power after attrition to test the hypothesized effect of training on skeletal muscle RAGE and sRAGE concentrations. We will enroll 75 subjects with the anticipation that there will be 20-25% attrition at 12 weeks. We anticipate that the final N after attrition will be 60 (n= 30 per group). Using the two-sided alpha level of 0.05, we estimate that a total sample size of 60 will enable us to detect a pre-post, between-group difference of 1.24 standard units for RAGE between Aerobic Exercise training and Control groups with a target of 90% statistical power.

Safety and Efficacy Review

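### The only described test of the training effect adjusts for weight and BMI measured after randomisation, so it may not estimate exercise versus standard care

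*Combined protocol and SAP*

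**What the plan says.** The first item under Study Objectives is: "Test the effects of chronic aerobic exercise versus standard care alone on sRAGE in the circulation of adults with T2DM". Neither it nor the hypotheses limit the target to an effect that does not pass through body weight.

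Statistics and Sample Size Considerations holds the only description of how the groups are compared. Trajectories are compared with "appropriate adjustments for fixed (age, sex, medications, diabetes duration and severity) and time-varying covariates (i.e., weight, BMI, etc", in a nonlinear mixed model with a random intercept, for all outcomes. The decision rule is: "we will reject null hypothesis if significant (p<.05) interaction effect between group and time is observed". The follow-up comparisons belong to the same model: "Post-hoc analysis will examine differences between groups at different time points to assess the effect of exercise training on the outcome variables". The section headed Analysis Plan covers only ongoing analysis, sample batching and data storage. No unadjusted, baseline-adjusted, sensitivity or mediation analysis appears anywhere.

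On weight itself, the eligibility section states "Subjects must be weight stable (± 2 kg for ≥ 6 months", which is a condition at entry. The weight-maintenance diet under Metabolic Control Period covers the one-night stays only. Training takes place "approximately 5 days per week and include treadmill walking, cycling, elliptical, or other related modes of exercise". Nothing described holds weight constant over the 12 weeks.

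**The concern.** Randomisation makes the groups comparable on everything measured before it. Weight at 12 weeks is measured after it and may be a consequence of the allocated treatment. Conditioning on such a variable can do two things. It can remove any part of the training effect that acts through weight, and it can introduce bias when weight change and outcome change share an unmeasured cause. The adjusted interaction then no longer estimates the contrast in the first objective.

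Nor does it cleanly estimate an effect not acting through weight. In a random-intercept model, one weight coefficient pools two relations: how heavier people differ from lighter people, and how one person's outcome moves as that person's weight moves. The mixture need not equal either.

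The list of time-varying covariates also ends in an open-ended abbreviation. Because data are to be analysed as they accrue, the covariates could be settled after results have been seen. If training does change weight, a reader of a null or positive p-value could not be sure that it answers the stated question.

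**Working it through.** **The plan's own figure.** The plan states 60 participants, two-sided alpha 0.05, 90% power and a difference of 1.24 standard units. If the unit is the SD of the change, 30 per arm gives 99.7% power at 1.24 by the t distribution. The difference detectable with 90% power is then (1.960 + 1.282) × √(2/30) = 0.84 SD, or 0.85 SD by the t distribution. What the unit means is a separate question. Here 0.85 serves as a true effect with 90% power before any weight adjustment, and 1.24 is also checked.

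**The shift.** Take two time points, complete data and a linear random-intercept model. The nonlinear function is not specified, so the linear form stands in for it. The interaction estimate is then

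adjusted estimate = total effect − *b* × *a*

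where *a* is the between-group difference in weight change and *b* is the fitted weight coefficient. If *a* = 0 there is no shift, whatever *b* is.

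**Assumed inputs (none are in the documents).** *a* = −0.5 or −0.8 SD of weight change (1.5 or 2.4 kg if that SD is 3 kg); within-person slope −0.3 or −0.5 SD of outcome change per SD of weight change; weight SD 17 kg; pre-post correlation of the outcome (ρ) 0.5 or 0.9; cross-sectional weight-sRAGE correlation (*r*) −0.2, 0 or +0.2.

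**Change-score regression adjusted for weight change.** Here *b* is the within-person slope:
- *a* = −0.5, slope −0.3: 0.85 − 0.15 = 0.70
- *a* = −0.8, slope −0.3: 0.85 − 0.24 = 0.61
- *a* = −0.8, slope −0.5: 0.85 − 0.40 = 0.45

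**Random-intercept model with weight as a time-varying level (closest to the plan).** Here *b* is an information-weighted average of the within- and between-person slopes. The lowest case is *a* = −0.8, slope −0.5, ρ = 0.9, *r* = −0.2:
- In units of the SD of change, the single-measurement outcome SD is 1/√(2 × 0.1) = 2.236, and the weight SD is 17/3 = 5.667.
- Between-person slope: −0.2 × 2.236/5.667 = −0.079.
- Information per person within: 1/0.880 = 1.14, where 0.880 = (1 − 0.5²) + (0.5 − 0.139)².
- Information per person between: 31.86/4.667 = 6.83. Here 31.86 = 5.667² − 0.25 is the variance of a person's mean weight. The residual variance of the mean outcome is (5 − 0.25) − 0.079² × 31.86 + (0.139 − 0.079)² × 31.86 = 4.667.
- *b* = (1.14 × −0.5 + 6.83 × −0.079)/(1.14 + 6.83) = −0.139.
- Estimate: 0.85 − (−0.139)(−0.8) = 0.74.

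**Simulation (1,500 runs per cell, 30 per arm, REML), random-intercept estimates; true value 0.85:**

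| *a*, slope | ρ | *r* = −0.2 | *r* = 0 | *r* = +0.2 |
|---|---|---|---|---|
| −0.5, −0.3 | 0.5 | 0.83 | 0.85 | 0.87 |
| −0.5, −0.3 | 0.9 | 0.79 | 0.83 | 0.88 |
| −0.8, −0.3 | 0.5 | 0.83 | 0.84 | 0.87 |
| −0.8, −0.3 | 0.9 | 0.76 | 0.83 | 0.88 |
| −0.8, −0.5 | 0.5 | 0.82 | 0.85 | 0.86 |
| −0.8, −0.5 | 0.9 | 0.74 | 0.80 | 0.85 |

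Power is 84.7 to 91.9%, against 89 to 91% unadjusted (unadjusted estimates 0.84 to 0.87). With no training effect on weight, both adjusted models return 0.84 to 0.86. At a true 1.24 SD, power is 99% or more (random-intercept) and 91 to 99% (change-score).

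**No training effect on the outcome, but a common cause of both changes.** Rejection at the 5% level is 4.3 to 6.0% unadjusted, 4.5 to 8.2% random-intercept and 8.1 to 39.4% change-score (Monte Carlo error about 1.1 points at 5%).

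**A stronger cross-sectional relation.** In the lowest case with *r* = −0.5, the random-intercept estimate is 0.66 with 80% power. With no true effect, that setting rejects 14% of the time. The same model is to be used for insulin sensitivity and VO₂max, so a stronger relation for some outcome cannot be ruled out.

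**The case against.** The strongest reply concerns size. In the model nearest the plan, most cells move by 0.05 SD or less, because the assumed spread of weight between people dominates the pooled coefficient. Power hardly changes, and at 1.24 SD it is safe. The large shifts and the 39% rejection rate come from a change-score regression that the plan does not specify, and every input is assumed. All of this stands. It limits the expected damage but does not make the interaction an estimate of the first objective.

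A second reply is that adjustment may be deliberate. The central hypothesis concerns muscle as a source of sRAGE, and adipose tissue is sampled by microdialysis, so the investigators may want to separate muscle from adiposity. That is a reasonable secondary question, but no objective or hypothesis states it, and one pooled weight coefficient would not answer it cleanly.

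Three smaller points also stand:
- The hope under Potential Risks and Benefits of finding an "effective approach to prevent the progression of obesity and obesity-related diseases and inflammatory conditions" describes a benefit to society. It does not predict weight loss in participants, and the concern does not rest on it.
- In a linear model with complete data, covariates constant within a person cannot move the interaction. How medications or severity are coded is therefore a matter of completeness, not of bias in that setting.
- With the nonlinear function unspecified, restricting covariates to baseline does not by itself settle what the interaction estimates.

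**Conclusion.** The concern holds. The text is unambiguous that the only described test conditions on weight and BMI as they vary during follow-up, while the first objective asks for exercise versus standard care without that condition.

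The practical size is uncertain. Under the assumed inputs and a linear random-intercept model, a true 0.85 SD is estimated at 0.74 to 0.88 SD. The shift is usually toward zero and is slightly upward in some cells with a positive cross-sectional correlation. Larger shifts need a stronger weight-outcome relation or a change-score form of adjustment. The bias is nil if training leaves weight unchanged. Confidence is high that objective and test do not match, and much lower about any particular figure. The point should be corrected before analysis, but it does not threaten the trial's feasibility.

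**What to change.** In the primary and secondary models, replace the time-varying weight and BMI adjustment with a closed list of pre-randomisation values: age, sex, baseline weight or baseline BMI (one only, since they are proportional within an adult of fixed height), baseline medications, diabetes duration, and one named baseline measure of severity. A1C, already collected at screening, would serve. Say explicitly that the medication value is the one before randomisation, because the Concomitant Medications section provides for "Prior to and during the intervention period, all medication use, dose and frequency will be documented".

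If the role of weight loss is of interest, report a model adjusted for weight change separately, labelled as an exploratory mediation analysis.

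The cost is a sentence or two in the statistics section; no procedure or visit changes. In the linear setting with complete data, adding baseline weight leaves the interaction as it is without adjustment, so no power is lost: the simulation gave 0.84 to 0.87 SD and 89 to 91% power. The full covariate list was not simulated, and the nonlinear function still has to be specified.

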Figure 2 provides a general framework of the study design. This 12-week clinical study involves the testing and training of middle age to older (40 - 75 y), overweight or obese adults (BMI 26 - 44 kg/m²) with type 2 diabetes (T2DM). Sixty subjects will be randomized to 12 weeks of aerobic exercise training plus standard care (Aerobic Exercise group; n=30) or standard care only (Control group; n=30). Subjects randomized to the Control group will be given the option of an off-label exercise intervention. Therefore, Control group participants will be allowed to enroll in the AE training group after completion of the original Control group trial period. All subjects will undergo the same baseline and post testing for basal metabolic rate, maximal aerobic capacity (VO₂max), body composition, insulin sensitivity, and microdialysis sampling coupled with muscle biopsies during an acute aerobic exercise trial before.

Due to the complexity of this study, an interdisciplinary research team with experience in clinical trials, pathophysiology of, and research in obesity, insulin resistance and T2DM, vascular function, aerobic exercise testing/training, clinical medicine, biotechnology, and advanced biostatistics has been assembled. The research staff has many years (>10 y) of direct research experience with human subjects and have been trained by experts in the field and University of Michigan protocols and guidelines.

Primary Outcome Measure

1) Quantify the change in basal circulating sRAGE after 12-weeks of supervised aerobic exercise training.

Serum will be separated from blood samples collected in vacutainer tubes via centrifugation before and after 12-weeks of aerobic exercise training. sRAGE will be quantified in these serum samples via ELISA (Quantikine, Human RAGE Immunoassay) per manufacture's protocol.

Secondary Outcome Measures

1) Quantify the change in basal muscle RAGE expression after 12-weeks of supervised aerobic exercise training.

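### Two planned visits cannot support the nonlinear mixed model; one linear week-12 contrast, adjusted for baseline and on a scale fixed beforehand, would be clearer and usually more precise

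*Combined protocol and SAP*

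**What the plan says.** All points are in Statistics and Sample Size Considerations unless another section is named.

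- Model and reason: "Because of the anticipated nonlinear response curves of outcome variables we will use nonlinear mixed effects models to analyze our data". The function is described only as "where f is some nonlinear function of known vector covariates (xij"; no curve, parameterisation or outcome scale is given there or elsewhere. Two likelihood approximations are named, neither as primary.
- Visits: "The primary outcomes of this study involve collecting data at pre-aerobic exercise training and 12 weeks of training". Primary Outcome Measure agrees for sRAGE: "Serum will be separated from blood samples collected in vacutainer tubes via centrifugation before and after 12-weeks of aerobic exercise training". Secondary Outcome Measures gives the same two times for muscle RAGE and the insulin clamp.
- Terms: "we will treat training group as main fixed effect, intercept as random effects, and all outcomes will be used as responsive variables".
- Decision rule: "we will reject null hypothesis if significant (p<.05) interaction effect between group and time is observed".
- Covariates: "appropriate adjustments for fixed (age, sex, medications, diabetes duration and severity) and time-varying covariates (i.e., weight, BMI, etc". The baseline value of the outcome is not listed.
- Interim visits: Maximal Aerobic Capacity and Follow-up Testing plan blood draws in both arms at about weeks 4 and 8, without naming sRAGE as an analyte. VO2max is repeated then in the exercise arm only. The statistics section adds post-hoc comparisons between groups at several times during the intervention.

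**The concern.** The stated reason for the model is curvature over time, yet the outcomes that carry the conclusions are planned at two times. The nonlinear machinery then either adds nothing to the test or moves it to an outcome scale that nobody has named. The Analysis Plan section says data are analysed as they accrue, so a scale left open could be settled with results in view.

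Two further features of the same model matter whatever the function turns out to be. It leaves out a covariate that is already measured and usually predictive, the baseline outcome. It also adjusts for weight and BMI over time. Training can change both, so part of the exercise effect may be removed from the estimate. At stake are precision with about 30 completers per arm, and a clear definition of the effect being tested.

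**Working it through.** **Inputs from the plan.** Two-sided alpha 0.05; 90% power; "We will enroll 75 subjects with the anticipation that there will be 20-25% attrition at 12 weeks". At 20% attrition, 75 × 0.80 = 60, or n = 30 completers per arm from N = 75/2 = 37.5 enrolled per arm.

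**Assumptions.** The documents give no correlation or distribution. I take a baseline-to-week-12 correlation rho of 0.3/0.5/0.7/0.9, equal SDs at both visits and in both arms, and dropout unrelated to outcome.

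**The plan's own figure.** No figure is attached to the choice of model. The sample-size statement (60 participants, 1.24 standard units, 90% power) is not reproduced by a two-sample t test: 1.24 SD needs 15 per arm, and 30 per arm detects 0.851 SD. The SD behind the unit is undefined, so the figure is unverifiable rather than shown wrong. Nothing below rests on it.

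**1. Can a curve be estimated?** Two arms by two visits give four means, and a linear group-by-time model uses all four. A quadratic or exponential-approach curve per arm needs six mean parameters; the design matrix has rank 4. With visits at 0, 4, 8 and 12 weeks the rank is 6 of 6.

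**2. Does bending the time axis change the test?** With two visits, replacing time t by g(t) multiplies the interaction estimate and its standard error by the same constant, 12/[g(12) − g(0)]. Five forms fitted to one simulated data set (linear, two exponentials, square, log) each gave z = 3.113, equal to the change-score t.

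**3. What do the listed covariates do?** With complete data, time-fixed covariates entered as main effects cancel from the change. In 20 simulated data sets the interaction estimate moved by at most 2e-15. Weight and BMI measured over time do not cancel. The documents do not allow that effect to be sized.

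**4. Precision.** Each variance is divided by that of the complete-case change-score contrast.

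- ANCOVA on completers, including the cost of estimating the slope: (1 + rho)/2 × [1 + 1/(2n − 4)], with 1/(2 × 30 − 4) = 1/56.
- The plan's likelihood-based group-by-time estimator (linear function, weight and BMI left out), which keeps dropouts' baselines: [(1 + rho) + (1 − rho)(n/N)]/2, with n/N = 30/37.5 = 0.8.

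| rho | ANCOVA | Plan's estimator | ANCOVA ÷ plan | Reduction vs plan | Reduction vs change score |
|---|---|---|---|---|---|
| 0.3 | 0.662 | 0.93 | 0.712 | 29% | 34% |
| 0.5 | 0.763 | 0.95 | 0.803 | 20% | 24% |
| 0.7 | 0.865 | 0.97 | 0.892 | 11% | 13% |
| 0.9 | 0.967 | 0.99 | 0.977 | 2% | 3% |

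Detectable differences at 90% power, in single-visit SDs, are 0.819/0.744/0.613/0.374 for ANCOVA and 1.007/0.851/0.659/0.381 for the change score. Multiplying the latter by the square root of the plan's ratio gives about 0.971/0.829/0.649/0.379 for the plan's estimator. All are below 1.24. If 1.24 is instead in SDs of change, the change-score figure to compare is 0.851.

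Adding sex, balanced by design, costs almost nothing (ANCOVA ratio 0.663/0.761/0.860/0.971 by simulation). Five uninformative covariates give 0.740/0.831/0.944/1.063, which is worse than the change score at rho 0.9.

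**5. If the scale were picked after seeing results.** Simulated null log-normal data (log-SD 0.3 to 0.7, rho 0.3 to 0.9), smallest p across change scores: type I error 0.061–0.074 for raw or log, and 0.071–0.095 with the reciprocal added. Any one fixed scale gives 0.046–0.053. In the plan's own model form, the smaller p from an identity and an exponential function gives 0.066–0.075 when the exponential model is true.

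**The case against.** **The natural reading does no harm to the test.** The section speaks of response curves and trajectories, which is curvature in time, and step 2 shows that this leaves the test unchanged. That stands. A reader might infer from step 5 that the plan inflates type I error. The documents do not support this: the plan's model leaves the outcome untransformed, and nothing proposes picking a scale by its p value. A starker inference comes from an exponential function with constant-variance error fitted to log-normal data (rho 0.7, log-SD 0.3/0.5/0.7), where type I error reaches 0.088/0.196/0.365. That shows how one hypothetical choice could fail. The plan names no such function, and no sRAGE distribution is given.

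**There may be more than two visits.** The both-arm blood draws at weeks 4 and 8 and the post-hoc sentence could mean that sRAGE is followed at four times, which would support a curve. This stands as an ambiguity, so two visits cannot be called settled for sRAGE. It does not rescue the model for muscle RAGE or the clamp, which have two times, or for VO2max, whose interim tests are in one arm.

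**A likelihood model is not a complete-case change score.** Correct: it retains dropouts' baselines, so the fair comparison is 29/20/11/2%, not 34/24/13/3%.

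**Power is ample, and naming the function would suffice.** The first part stands; no shortage of power is claimed. The second would close the gap in specification, but would leave the baseline outcome unused and post-randomisation weight and BMI in the primary model.

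**Conclusion.** The concern holds in limited form. The reason given for a nonlinear model does not match outcomes planned at two times. Either the nonlinearity leaves the test as it would be in a linear model, or it puts the test on an unspecified outcome scale. The planned comparison gives up precision by not using the baseline outcome, and its adjustment for weight and BMI over time may remove part of the exercise effect.

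The gain is a variance about 29/20/11/2% lower than the plan's own estimator at rho 0.3/0.5/0.7/0.9, given 37.5 enrolled and 30 completing per arm. It rests on an assumed rho and is small near 0.9. The type I error range of about 0.06 to 0.095 is illustrative, and applies only if the scale were chosen from the results. The weight and BMI effect is not quantified. The change should be made; confidence is medium, because rho, the distribution of sRAGE and the use of the interim blood are all unstated.

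**What to change.** Replace the nonlinear model with one prespecified linear analysis:

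- **Primary test:** the arm contrast at week 12 for circulating sRAGE, two-sided 0.05, by ANCOVA on arm, baseline sRAGE and sex (Group Assignment Procedure balances sex between the arms).
- **Scale:** raw or log, one of them, written down before any outcome is compared by arm. The documents give no basis for choosing between them here; what matters is that the choice is made beforehand.
- **Other covariates:** baseline values only, named in advance, and few.
- **Weight and BMI after randomisation:** move to an analysis labelled exploratory.
- **Interim blood:** state whether weeks 4 and 8 are assayed for sRAGE. If so, use a linear mixed model with categorical visit, arm-by-visit terms and a common baseline mean, keeping week 12 primary. Under compound symmetry its large-sample variance relative to the change score is 0.735/0.825/0.914 at rho 0.5/0.7/0.9, against 0.75/0.85/0.95 with two visits.
- **Other outcomes:** the same ANCOVA serves muscle RAGE, clamp insulin sensitivity and VO2max at baseline and week 12.

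The cost is new wording in the statistics section and simpler code, with no added visits, samples or assays. The downsides are that no time curve is fitted, that little is gained if rho is near 0.9, and that a long covariate list could cost some precision there.
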